Eligibility criteria- possibility that participants may be recruited that do not match the eligibility criteria (or include patients with exclusions criteria)	Recruit high risk patients, or those that do not have spirometry confirmed COPD.	Site training and use of an eligibility form will contain tick boxes containing individual statements regarding the inclusion/exclusion criteria. Spirometry will be carried out at the baseline visit to confirm COPD diagnosis.	Central monitoring will verify that eligibility was assessed prior to trial entry, on a proportion of patients

Possible Risk Design and methods	Describe the risk	Can the risks be reduced? What would you do?	How would you monitor the study to address concerns?
		Participants will be familiarised with the environment, and informed of safe areas as well as areas where there may be obstacles or equipment.	Adverse events will be documented in the patient file and on an incident log.
	Participants colliding with each other	Appropriate distances will be maintained between participants so that exercises can be carried out safely.	Rehabilitation specialists will receive additional training if safety issues are identified
Patient visits	Tripping over equipment Participants misusing equipment	Participants will be trained on how to use the equipment safely.	Patients will be re-trained on how to use equipment.
	Participant experiences a negative response to physical activity – excessive breathlessness or fatigue or dizziness	Rehabilitation specialists will carry out a pre- rehabilitation session with each participant to prescribe an individualised and safe exercise programme which is based on the patient's exercise capacity. Participants will be informed of how to respond if they experience a negative response to the exercise programme. A rehabilitation specialist will be available at each exercise session, and will observe all patients.	Rehabilitation specialists will re- assess on the patient's exercise prescription, and consider the need for changes. Researchers to assess incident logs to identify training needs of rehabilitation specialists.
Data collection methods	The risk of incomplete data is low as most CRFs will be completed face to face with the participant. There may be a small risk of incomplete data	The CRFs have been kept to a minimum and have been well reviewed, so complexity is reduced.	Early monitoring of data return may identify any issues
Database systems • System complexity • User training	due to the length of the questionnaires. Risk of transcription errors from paper to database.	Some data validation is built into the database so range, date and logic checks are performed for some of the entries.	Data entry quality checks will be performed on a sample of CRFs.

Risks Assessment Report Review (Main Coordinator/Chief Investigator)

Name	Signature	Date

[figure not shown]
Appendix 3

Incident log

Date	Participant	Incident details	Action	Follow-up	Outcome	Rehabilitation	Signature
	ID		taken	action (if	(with	specialist	
				applicable)	date)	details	

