Focus group discussion A discussion guide (appendix 1) will be used in all three focus groups to consider which are the essential elements of a PR programme for delivery, and the components that would be tailored to meet the needs of COPD patients in Georgia. For example, this will include assessing the need for: training on inhaler technique, medication adherence, action planning (managing COPD flare-ups)) and how or who should provide the education/information (for example, education on smoking cessation as part of the PR or whether there should be referral to a specialist smoking cessation programme). The discussion guide will also explore the appropriate and acceptable delivery methods of the PR programme for example, the setting (e.g. hospital vs. home), equipment (e.g. treadmill vs. outdoor walking), length of the programme (for example, 6-weeks vs. 8-weeks) and the duration of each PR session. The discussions will use the APEASE criteria - affordability, practicability, effectiveness (and cost-effectiveness), acceptability, side-effects (and safety), and equity (14).

Phase 2: Randomised controlled feasibility trial

Study setting

The study will primarily recruit participants from the Chapidze Emergency Cardiology Center, Tbilisi. This will be supplemented by recruiting for primary care (GP practices), if necessary.

Eligibility criteria

Inclusion:

- MRC 2+
- Confirmed COPD diagnosis based on spirometry (predicted ratio of FEV₁/FVC of 0.70)
- Patient must be able to walk 10 meters independently
- Patient able to exercise with some degree of independence, and within a group setting

Exclusion:

- Musculoskeletal or neurological conditions that prevent exercise
- Unstable CVD (e.g. unstable angina, aortic valve disease, unstable pulmonary hypertension)
- Severe cognitive impairment
- Severe psychotic disturbance
- · Contagious infectious disease
- Very poor balance

Randomisation

Randomisation to one of the two groups will be performed using an electronic database (REDcap); allocation will be based on a 1:1 ratio.

Subsequent to randomisation, patients will be asked to complete all baseline measures and questionnaires.

Intervention: pulmonary rehabilitation programme

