A pre-rehabilitation one-to-one assessment will be booked at a time convenient for the patient. The aim of this assessment will be to orientate the patient to the PR intervention and tailor their exercise programme. For this, the ISWT, perceived exertion and breathlessness scale will be used to prescribe the intensity of the exercise component of the PR programme. Patients will be prescribed 65 - 85% of their maximal baseline ISWT performance (can be lower in deconditioned patients) (15).

The adapted PR programme will consist of two main components: exercise and education on the management of COPD. The description, content and frequency of these components will be determined during phase 1 of this project (cultural tailoring).

Control group

Participants randomised to the control group will be offered to attend a 2-3 hour educational session. This will be carried out by the rehabilitations specialists 6-months after study enrolment, once follow-up is complete.

Outcome measures

Data will be collected from patients at the end of the PR programme (6 - 8 weeks) and at sixmonths.

Feasibility study outcomes will include: delivery with fidelity, acceptability to participants, recruitment rate, follow-up rate at 6 months, adherence to intervention, ability to carry out trial procedures, feasibility of methods to measure costs of PR, other COPD-related health care utilisation and patient-incurred costs

Outcome measures to inform a future trial to evaluate clinical and cost effectiveness: HRQoL (SGRQ and EQ-5D-5L); exercise capacity measured by the ISWT; smoking status validated by cotinine; COPD Assessment Test (CAT); self-reported physical activity (IPAQ); self-efficacy; anxiety and depression

(PHQ-9 and GAD-7); self-reported exacerbations; health care utilisation including hospital admissions; and costs/resource use incurred by patients.

Participant timeline

Participants randomised to the intervention group will be invited to a baseline visit/one-to-one prerehabilitation assessment. The number of PR intervention visits per week, and the total length of the PR programme will determined after phase 1 of the project (focus group discussions).

Participants randomised to the control group will be invited to four visits: baseline visit, follow-up visits (end of programme and 6-months) and a 2-3 hour educational and exercise session (6 months).

Sample size

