Data from literature suggests that pilot studies that aim to inform larger trials should include \geq 30 participants to estimate a parameter (16). Based on this, 30 patients will be included in each arm of the trial (total: n=60).

Recruitment

Eligible COPD patients, attending the Chapidze Emergency Cardiology Center, will be invited to take part in the feasibility trial. Those who work in the clinic (e.g. respiratory consultant, or consultant's assistant) will either phone existing clinic patients to provide information about the study, or inform those who are attending their clinic appointment. To encourage recruitment of a range of socioeconomic groups, patients will be recruited from primary care and other hospitals within Tbilisi.

Patients who are interested will be provided with the study invitation documents (including participant information sheet and reply slip) via email or post (through the DHL service, as the national postal service is unreliable). These documents will be provided at the time of the clinic appointment, for those who indicate an interest in-person.

Methods: Data collection, management, and analysis

Data collection methods

Phase 1: Tailoring pulmonary rehabilitation to the Georgian context

Three focus group discussions will be carried out, lasting up to 2 hours each, and will be audio-recorded. Informed consent will be gained at the time of the focus group session. No other research visits will be involved in the phase of the study.

Phase 2: Randomised controlled feasibility trial

Study assessment 1

The baseline research assessment is likely to last approximately 90 - 120 minutes, and include the following components:

Eligibility check: this will be assessed based on the inclusion/exclusion criteria above.
 Spirometry will be carried out by the respiratory team at the Chapidze clinic, who will confirm COPD diagnosis.

- 2. Informed consent: Participants will have the opportunity to ask any questions before completing the consent form with the researcher. As well as consenting to the main study, participants will asked to consent to being contacted and take part in the qualitative interviews linked to this study.
- 3. Completion of the case report form (CRF), which will include the following:
 - a. Documenting patient details (initials, age, sex, ethnicity and employment status)

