 - b. Conducting the Incremental Shuttle Walking Test (ISWT): to be carried out twice; distance walked to be documented in meters; collect various measures pre and post each test (blood pressure, heart rate, oxygen saturations, Borg dyspnoea and RPE scores); record reason for cessation (e.g. breathless, dizziness, painful legs).
 - c. Self-administered participant questionnaire booklet: sociodemographic data (age, sex, ethnicity, education level, marital status, number of dependents; number of adults in the household; and employment); comorbidities; medications; level of dyspnoea (MRC score); smoking status; quality of life and disease specific questionnaires (EQ-5D-5L; St George's Respiratory Questionnaire [SGRQ]; and COPD Assessment Test [CAT]); anxiety and depression (GAD 7 and PHQ-9); self-reported physical activity levels (International Physical Activity Questionnaire [IPAQ]); and health service use (hospitalisations).
 - d. Measuring height and weight to calculate body mass index (BMI)
 - e. Saliva or urine sample to measure cotinine (nicotine levels)
- 4. Randomisation to the treatment or control group

The baseline assessment will be carried out by a member of the research team (exception: the ISWT will be carried out by the trained rehabilitation specialist(s)). The researcher will record all study data on CRFs to ensure standardised data collection/recording. On completion, the researcher will enter the data on to the secure REDcap electronic database.

Study assessment 2

At the end of the PR programme, participants will be invited to a second study assessment. This will include collecting similar data as the baseline assessment:

- 1. Conducting the ISWT (once), and collecting all pre and post-test measures (as detailed above), by the rehabilitation specialist
- 2. Self-administered participant questionnaire including the following: level of dyspnoea (MRC score); smoking status; quality of life and disease specific questionnaires (EQ-5D-5L; St George's Respiratory Questionnaire [SGRQ]; and COPD Assessment Test [CAT]); anxiety and depression (GAD 7 and PHQ-9); self-reported physical activity levels (International Physical Activity Questionnaire [IPAQ]); health service use (hospitalisations); patients costs (for those attending the PR programme); and injuries or health issues as a result of the PR programme.
- 3. Saliva or urine sample to measure cotinine (nicotine levels)

Study assessment 3

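### The protocol places the baseline measures both after and before randomisation, and needs to state one order with randomisation last

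*Protocol*

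**What the plan says.** Three places in the Phase 2 part of the protocol bear directly on the order.

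- **Randomisation.** After describing 1:1 allocation through REDCap, the section ends: "Subsequent to randomisation, patients will be asked to complete all baseline measures and questionnaires".
- **Participant timeline.** For the PR arm: "Participants randomised to the intervention group will be invited to a baseline visit/one-to-one prerehabilitation assessment". For the control arm: "Participants randomised to the control group will be invited to four visits: baseline visit, follow-up visits (end of programme and 6-months", followed by the education and exercise session.
- **Data collection methods, Study assessment 1.** The list is introduced by "The baseline research assessment is likely to last approximately 90 - 120 minutes, and include the following components". Step 1 is the eligibility check, including spirometry. Step 2 is informed consent. Step 3 is the case report form, with two ISWTs, the questionnaire booklet, height and weight, and a cotinine sample. Step 4 is "Randomisation to the treatment or control group".

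Two other places help in reading these. Appendix 2 (risk assessment) puts spirometry at the baseline visit, but it also names consent missing before trial entry as a risk and has central monitoring check that eligibility was assessed before entry. The Intervention section describes the pre-rehabilitation assessment as a one-to-one appointment, booked to suit the patient, that introduces PR and tailors the exercise programme.

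**The concern.** Staff working from the Randomisation section would randomise and then take baseline measures. Staff working from Study assessment 1 would do the reverse. The order of these steps is core protocol content and cannot be left to an analysis plan.

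Two things are at stake if randomisation comes first.

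1. **Quality of the baseline data.** The SGRQ, EQ-5D-5L, CAT, PHQ-9, GAD-7 and IPAQ are self-reported. The ISWT depends on effort and is run by rehabilitation specialists, the same staff group that delivers the programme. Knowing the allocation can influence all of these, so a baseline difference between arms could no longer be put down to chance. That weakens data whose stated purpose is to inform a future trial.
2. **The feasibility outcomes.** Process measures include the percentage of complete baseline data and the follow-up rates at end of programme and 6 months. With a gap between randomisation and baseline, people can drop out in that gap. They then count among those randomised but have no baseline record.

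**Working it through.** No arithmetic applies, because the point concerns the order of procedures. The protocol gives no figure from which a bias could be derived. Its sample-size figure (30 per arm, 2 × 30 = 60) is consistent and plays no part here. The check is to set the texts side by side.

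| Source in the protocol | Order implied |
|---|---|
| Randomisation | randomise → all baseline measures and questionnaires |
| Participant timeline, PR arm | randomise → baseline visit, written together with the pre-rehabilitation assessment |
| Participant timeline, control arm | randomise → baseline visit, listed first of four visits |
| Study assessment 1 | eligibility → consent → baseline measures → randomise |
| Appendix 2 | consent and eligibility before trial entry |

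**Step 1: is the conflict real?** The Randomisation sentence covers all baseline measures, and Study assessment 1 places all of them before allocation. No single schedule satisfies both. The Participant timeline wording leans towards the first order, so the sentence is not obviously an isolated slip.

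**Step 2: would allocation be known at baseline under the first order?** The protocol does not say when allocation is disclosed. It describes no blinding, however, and the invitations differ by arm. For the PR arm, the baseline visit is also written together with an appointment whose purpose is to introduce PR. Knowledge of allocation is therefore probable, but it is an inference.

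**Step 3: what happens to the denominators?** If randomisation is the last step of the assessment, everyone randomised has already attended baseline, and incomplete baseline data means missing items or tests. If randomisation comes first, the randomised group can also include people with no baseline visit at all. Baseline completeness and follow-up, taken over those randomised, would then include losses that the other order excludes.

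**Step 4: which planned results are exposed?** Statistical methods plans recruitment and follow-up rates with 95% confidence intervals, and HRQoL by arm at the end of PR and at 6 months. It states no change-from-baseline or baseline-adjusted analysis. The direct exposure is therefore in the feasibility rates and in the baseline data passed to a future trial. A bias in a stated effect estimate cannot be shown.

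**The case against.** **Consent and eligibility.** A reader might infer that the protocol also puts consent and eligibility after randomisation. The Participant timeline sends randomised people to a baseline visit, Study assessment 1 places "Eligibility check: this will be assessed based on the inclusion/exclusion criteria above" and "Participants will have the opportunity to ask any questions before completing the consent form with the researcher" inside that visit, Appendix 2 puts spirometry there too, and no separate screening visit is described. Read together, these do imply it. But no place says so. The inference takes steps 1 and 2 from a list whose step 4 is randomisation and sets step 4 aside. Appendix 2 shows the opposite intention on both consent and eligibility. This is a reason to clean up the wording, and the documents do not support charging the plan with randomising before consent.

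**The Participant timeline is weak evidence.** Its sentences can be read as a list of visits by arm, and the slash in the PR-arm sentence need not mean one combined visit, since the Intervention section has the pre-rehabilitation assessment booked individually. That is a fair reading, and it softens this support. It does not touch the Randomisation sentence, which is explicit about order.

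**The trial is not powered for effect.** This is true, and with no baseline-adjusted analysis stated it rules out putting a number on bias in the SGRQ or any other result. Any such number would rest on an assumed shift for an analysis that the protocol does not name. It is no defence for the feasibility rates, which are what the trial sets out to estimate, nor for the trial's aim of testing whether its procedures can be carried out.

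**Conclusion.** The protocol contradicts itself on whether baseline measures come before or after randomisation, and this should be corrected before anyone is randomised, because a baseline taken after allocation cannot be repaired later.

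The contradiction itself rests on explicit text. The consequences are conditional: they arise only if the order in the Randomisation section is followed, and the effect on self-report and effort further assumes that participants or assessors know the allocation by then. No numerical size can be given from the document. The order in Study assessment 1 is the more detailed account and agrees with Appendix 2, so it is the natural one to keep.

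**What to change.** 1. In Randomisation, delete the final sentence. State instead that REDCap randomisation is the last step of Study assessment 1, after the eligibility check, consent and all baseline measures, including both ISWTs. This keeps the sequence already listed there.
2. In Participant timeline, state that all participants complete the same baseline assessment before randomisation, and that only those then allocated to PR have the pre-rehabilitation assessment, which uses the baseline ISWT already recorded.

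**Cost.** Mainly wording; no extra participants are needed. If the sponsor intended one combined baseline and pre-rehabilitation visit for the PR arm, the pre-rehabilitation assessment becomes a separate step after randomisation. It could be held the same day or at the individually booked appointment that the Intervention section already describes; in the second case it may mean an additional attendance for up to 30 participants.

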Since 2013 the government of Georgia has launched a Universal Healthcare Program, which ensured universal coverage of healthcare services for Georgia's population (4). More than 90% of the Georgian population are beneficiaries; the rest are covered through private insurance services (5). The program covers planned and emergency outpatient and inpatient services and basic medication for vulnerable populations (5). Although the Universal Healthcare Programme covers all health care service costs and part of the cost of medicines few COPD patients receive medication because medications are only reimbursed for hospital inpatients and some vulnerable groups; most people have to pay for their medication.

Pulmonary rehabilitation (PR)

International scientific evidence suggests that pulmonary rehabilitation (PR) has physiological and psychosocial benefits (6), when delivered post-admission for an exacerbation PR reduces hospital admissions and may reduce mortality (7). PR has been shown to be cost-effective in high income country settings (8). A systematic review of trials showed that PR helps with fatigue and breathlessness, and improves quality of life and exercise capacity of patients, with evidence that at least 4 weeks of exercise training were needed for benefits to be observed (6), whilst the ATS/ERS Statement on PR recommend a minimum of 6 weeks of exercise training (9) and more recent guidance recommends a minimum of 8 weeks of exercise (10). Exercise is recommended to be 2-3 times per week and is often delivered in two supervised or monitored sessions, with a third unsupervised session. The most effective components within PR, its length and location, degree of supervision and intensity of training required is not clear (6), although exercise is considered to be the most important component (11). Recent recommendations from The ATS/ERS state that "to qualify as PR, programs must include, at a minimum: a structured and supervised exercise program for patients with a variety of respiratory conditions, a patient education/behavioural program intended to foster health enhancing behaviour, patient assessment and outcomes measures, and provision of recommendations for home-based exercise and physical activity" (10).

Rationale for the study

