Patients will be invited to attend a final follow-up assessment, after 6 months, to collect the following data:

- 1. The ISWT (once), and collecting all pre and post-test measures (as detailed above, and to carried out by a rehabilitation specialist)
- Self-administered participant questionnaire including the following: level of dyspnoea (MRC score); smoking status; quality of life and disease specific questionnaires (EQ-5D-5L; St George's Respiratory Questionnaire [SGRQ]; and COPD Assessment Test [CAT]); anxiety and depression (GAD 7 and PHQ-9); self-reported physical activity levels (International Physical Activity Questionnaire [IPAQ]); and health service use (hospitalisations)
- 3. Saliva or urine sample to measure cotinine (nicotine levels)

Study assessments 2 and 3 will be carried out by a member of the research team.

Process measures

To be able to assess the feasibility of delivering the PR intervention, the following will be measured:

- 1. Fidelity of delivery of the programme by the rehabilitation specialists: the aim will be to assess whether patients are achieving their prescribed exercise goals which have been set by the rehabilitation specialist. For this, a member of the research team will examine the following patient data over six PR sessions: attendance to all PR sessions (noting number of missed sessions); completion of all prescribed exercises; achieved all sets/repetitions/exercise duration prescribed for each exercise; achieved the recommended exertion score (Borg score); and exercise prescription review (changes by physios based on patient progress). This data will be completed by the patient at each visit, and stored in their research file.
- 2. Participant adherence to the intervention: number of sessions attended; completion of the PR programme; where sessions were carried out (home/clinic) and how many session within each setting; consistent achievement of prescribed goals (e.g. sets/reps/exertion); and education session attendance. This data will be extracted for the patient's research file.
- 3. Ability to carry out trial procedures: baseline data (% complete); follow-up rates (end of programme and 6-months); recruitment rate, and comparison of the characteristics with those who declined to take part; and completeness of data entry.
- 4. Reach: characteristics of the participants; ability to recruit the more socio-economically disadvantaged members of the population; and assessment of geographical reach

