We will report recruitment and follow-up rates, with 95% confidence intervals, as a measure of feasibility of the trial. Although the trial will not be powered to detect a difference between intervention and wait-list control, we will calculate the HRQoL at PR end and 6 months for those allocated to each group; 95% confidence intervals will be provided for estimates obtained. The economic analysis will report questionnaire completion rates, and a cost-consequences analysis. This will include a descriptive analysis of health care costs and EQ-5D-5L scores and an initial estimate of the cost of PR, taking into account the duration of the intervention, format of sessions and number of sessions attended by each participant.

Qualitative data

The Framework approach to data management and analysis will be used for the interviews and focus groups (17).

Methods: Monitoring

Data monitoring

The study will be overseen by a Study Steering Committee, consisting of one representative from each of the following stakeholder groups: patient, clinician/policy maker, research team and, the Breathe Well executive committee. In addition there will be two representatives from the International Scientific Advisory Committee, one of whom will act as chairperson. The Study Steering Committee will meet on a 6-12 monthly basis, as required.

The research team will hold monthly meeting with the Breathe Well executive committee, to discuss current progress and any issues arising.

Harms

The focus group discussions, physiological and questionnaire-based measures pose no risk to the participants.

Non-serious adverse events

The risk of harm associated with study procedures and the intervention are considered to be very low. To further minimise the risk of events, we will:

- 1. Ensure patients meet the eligibility criteria
- 2. Carry out a risk assessment (e.g. of the venue, risks to patients and staff) see appendix 2
- 3. Staff will be trained to manage any risks that are identified in the assessment

Due to the low risk in this study, only the following non-serious adverse events will be collected which will form part of the study outcomes:

- Musculoskeletal injury as a result of the intervention
- Other minor injuries as a result of the intervention
- Non-serious medical events during the rehabilitation that do not require admission to hospital, e.g. participant had to stop due to angina attack that resolved with medication.

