Opportunities to exercise after pulmonary			
rehabilitation			
Confidence, self-efficacy and self-			
management			
Loving relationship/sexuality			
Goal setting and rewards			

- 9. Who would be best placed to deliver the PR programme (who has the skill-set)?
 - a. The exercise sessions
 - b. The educational sessions
- 10. Involvement of other persons or professionals in the delivery of the PR programme (other than the rehabilitation specialist)?
- 11. Forms of social support during the programme?
 - a. Internet blogs or groups?
 - i. Internet access available for most?
 - b. Meetings/events with other COPD patients (e.g. support groups)?

Cognitive adaptations

NOTE: when exploring cognitive adaptations, to also assess whether any cross-culture differences (people in other parts of Georgia)

- 12. Language(s)?
 - a. Group sessions
 - b. Material (handouts, leaflets etc)
 - c. Electronic material
- 13. Reading level adjustments?

NOTE: share PR information/handouts/videos with the groups

- a. Literacy levels
- b. Literal translation practical?

- 14. Technological components (videos/PowerPoint slides/support groups)
 - a. IT access and literate?
- 15. Use of non-offensive language

NOTE: video clip about encouragement during PR programme

- a. Would patients be comfortable with such encouragement?
- b. Using the Borg scale as a method of assessing exercise intensity

Physical barriers

16. Travel

- a. Would this be an issue?
- b. Access from rural areas?
- c. What would patients think about a home-based element?

17. Employment?

a. Timing of the programme

Outcome measures

- 1. Outcome measures to be assessed?
 - a. Any culturally appropriate outcomes to assess intervention effectiveness?
 - b. Current proposed measurement tools appropriate? (shuttle walk, MRC dyspnoea, Hospital Anxiety and Depression Scale, SGRQ, CAT, health service use, exacerbations, cotinine test, self-reported physical activity)

Other issues

- Other social and cultural issues
- Beliefs about breathlessness and exercise
- · Gender issues?
- Form of relaxation?
- Cohort or rolling programme?
- Outside a trial setting, what are the facilities for assessments to ensure a diagnosis of COPD and of exercise capacity to tailor the physical activity to the individual
- Can national audit be built into the system? Assessments at baseline and follow-up with standard assessments to enable comparison between programmes.

Appendix 2

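### Exacerbations and self-efficacy are named as outcomes but listed at no assessment, and patient costs are listed once, for programme attenders only

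*Protocol*

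**What the plan says.** The Outcome measures section of the protocol sets data collection at the end of the programme (6 to 8 weeks) and at six months. Its list of outcomes to inform a future trial includes "self-reported physical activity (IPAQ); self-efficacy; anxiety and depression" and, at the end, "self-reported exacerbations; health care utilisation including hospital admissions; and costs/resource use incurred by patients". Among the feasibility outcomes, the same section places the feasibility of measuring COPD-related health care use and patient-incurred costs. The Summary repeats exacerbations, health service utilisation and patient-incurred costs.

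The Data collection methods section then sets out each visit item by item. The baseline booklet and the six-month questionnaire end in the same way: "self-reported physical activity levels (International Physical Activity Questionnaire [IPAQ]); and health service use (hospitalisations"). The end-of-programme questionnaire (Study assessment 2) has "health service use (hospitalisations); patients costs (for those attending the PR programme") and an item on injuries or health problems caused by the programme.

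Under Statistical methods, the economic analysis is a cost-consequences analysis, of which the protocol says "This will include a descriptive analysis of health care costs and EQ-5D-5L scores", together with a first estimate of what the programme costs.

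**The concern.** The outcome list and the visit lists are two statements of the same data collection, and they disagree. The case report forms and the database will be built from the visit lists. An outcome missing there is likely to be missing from the data, and a later analysis plan cannot restore it.

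Two things are at stake. A feasibility trial should show whether each outcome proposed for the main trial can be collected, and an outcome with no collection point is not tested at all. Also, whether utilisation and patient costs can be measured is itself one of the questions this trial asks. A method not tried in controls or at six months leaves that question open for half the participants and for the later time point.

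**Working it through.** No formula is involved. The check sets each outcome in the Outcome measures section against Study assessments 1, 2 and 3, and then against Process measures, Harms and Statistical methods.

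| Outcome | Baseline | End of programme | 6 months |
|---|---|---|---|
| SGRQ, EQ-5D-5L, CAT, IPAQ, PHQ-9, GAD-7 | listed | listed | listed |
| ISWT | listed | listed | listed |
| Smoking status with cotinine | listed | listed | listed |
| Health care utilisation | hospitalisations only | hospitalisations only | hospitalisations only |
| Patient costs | not listed | programme attenders only | not listed |
| Self-reported exacerbations | not listed | not listed | not listed |
| Self-efficacy | not listed, no scale named | not listed | not listed |

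Process measures add none of the missing items; they cover fidelity, adherence, trial procedures, reach and acceptability. Outside the outcome lists, exacerbations appear only in the background, the Phase 1 discussion guide and its table of self-management topics. Self-efficacy appears only in that table.

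Size, taking the visit lists at face value:

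- Inputs: 30 participants per arm, 60 in total (Sample size section), and two follow-up visits.
- Possible follow-up records per outcome: 60 × 2 = 120, of which 30 × 2 = 60 are from controls.
- Exacerbations: 0 of 120. Self-efficacy: 0 of 120, and 0 of 60 at baseline.
- Patient costs: at most 30 × 1 = 30 of 120, or 25%. Controls contribute 0 of 60, and the six-month visit 0 of 60. Any intervention participant who does not attend lowers the 30.
- Hospitalisations: up to 120 of 120, in both arms.

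For the economic analysis, EQ-5D-5L and hospitalisations can therefore be described by arm. Contacts short of admission and patient costs cannot.

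**The case against.** The strongest reply is that the follow-up lists are introduced with open wording, and assessment 2 is described as resembling the baseline. The lists may be summaries, and the Phase 1 discussion guide does mention exacerbations among the proposed measures. A reader might infer from the lists that these outcomes will never be collected. The documents do not support that; they support only that no assessment lists them. Even so, the lists are specific to each visit: costs and injuries are added at assessment 2 and dropped at assessment 3, and every other future-trial outcome is listed at all three. A team working from this text would probably leave the items out.

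Second, the cost item may mean only the cost of attending the programme. Controls would then have nothing to report, and 30 of 120 would not be a fair fraction for that item. This reading stands as possible. It does not rescue the broader outcome of costs and resource use incurred by patients, which would then have no listed item in either arm.

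Third, a reader might infer that none of the outcomes in the quoted run can be reported by arm. That is wrong for hospital admissions. The serious adverse event form also asks for a diagnosis, so an exacerbation leading to admission might be traced there. One treated outside hospital would not be, because the non-serious events to be collected are limited to injuries from the intervention and medical events during rehabilitation.

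Fourth, medicines are recorded only at baseline, while the background says "most people have to pay for their medication". It is tempting to count this as another missing outcome, but medication use is not named as an outcome, so it is not counted here.

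Two nearby loose ends are separate and minor: no step is described for recording the characteristics of people who decline, and the Phase 1 guide names an anxiety and depression scale that the trial does not use. Neither bears on this point.

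**Conclusion.** The inconsistency is real and should be fixed. Two named outcomes have no listed collection point and one of them has no instrument. A third, patient costs, is listed at one visit for part of one arm. A fourth, health care utilisation, is narrowed to hospitalisations although the outcome's wording is wider.

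The sizes given (0 of 120, 0 of 120 and at most 30 of 120) assume that the case report forms follow the visit lists and that all 60 participants are recruited and followed up. If the forms already hold these items, the defect is confined to the protocol text and is cured by listing them.

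The point stops short of a threat to the trial's main results. Recruitment and follow-up rates and HRQoL by group, which Statistical methods commits to reporting with confidence intervals, are unaffected. The protocol does not promise a between-arm comparison of patient costs, and it does not rank exacerbations above the other outcomes for a future trial.

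**What to change.** At assessments 2 and 3, in both arms and whether or not the participant attended the programme, add:

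- the number of self-reported exacerbations since the last visit;
- a short list of COPD-related health care contacts other than admissions;
- out-of-pocket costs to the patient.

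Keep the cost of attending the programme as a separate item for attenders, so that it is not confused with general patient costs. Name a self-efficacy scale and schedule it at all three visits, or delete that outcome. Delete likewise any other outcome that the team decides not to collect, so that the Summary, the Outcome measures section and the visit lists agree.

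The cost is a modestly longer questionnaire. This matters somewhat: baseline is already expected to take 90 to 120 minutes, and the risk assessment in Appendix 2 names questionnaire length as a possible cause of incomplete data. The follow-up items should therefore be few and short, and deletion is an acceptable alternative to addition. No change to sample size, visits or treatment is needed.
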